11.2 Potential Benefits to Others

Endometriosis is a devastating disease that affects up to 10% of reproductive aged women. The pathophysiology of endometriosis is not well understood, however, there is strong evidence that inflammation plays a large role in the symptoms associated with endometriosis. Current management strategies often result in the addition of opioid-based treatments. Given the current opioid epidemic, it is important to consider non-opioid based therapies. CBD has shown promise in other pain related disorders and may potentially decrease pain and improve the quality of life and sexual function in women with endometriosis. Endometriosis has been associated with a significantly decreased quality of life and recognized as a disease with a high economic burden.

12.0 Sharing Results with Subjects

N/A

13.0 Subject Payment and/or Travel Reimbursements

Subjects will receive \$175 at the completion of the study - \$50 per visit after the screening visit and \$25 for the post treatment visit. Subjects that participate in the pharmacokinetic arm of this study will be compensated an additional \$500. The subjects will spend 24 hours in the Clinical Research Center with an additional visit at 48 hours. They will be compensated at a rate of \$20 per hour for their time.

The payment will be provided by an external company, Greenphire Clincard. Details regarding compensation for patients are outlined in the Consent Form as follows:

You will receive \$50 per visit after the screening visit and \$25 for the post treatment visit for your participation in this research study for a total of \$175. If you do not complete the study for any reason, you will be paid for the visits you have completed. The payment will be provided by Greenphire Clincard (see below)

If you choose to complete the optional pharmacokinetic portion of this study, you will be compensated an additional \$500.

This reimbursement will be issued by an external company called Greenphire, which will issue your reimbursement. You will be issued a ClinCard, which is a debit card that your funds are loaded onto and can be used at your discretion. The research team will give Greenphire some personal information about you, as described below. Greenphire will only use your personal information to process this reimbursement and will not share it with anyone for any other purpose. Details of the debit card system are explained on an additional sheet. If you lose the card, you may be responsible for the replacement fee.

When a visit is completed, funds will be approved and loaded onto your card. The funds will be available within 2-3 business days. In order to assign a ClinCard to you and load funds onto the ClinCard, Greenphire will need your Study/Subject ID, Name, Address, and Social Security Number.

You will have the option to receive updates related to payment alerts via text message and/or email message. Standard text messaging rates will apply. In order to send you messages Greenphire will need your Mobile Phone Number and/or E-mail Address. Payment received as compensation for participation in research is considered taxable income. If payments from Greenphire exceed \$600 in any one calendar year, Greenphire will file a 1099 (Miscellaneous Income) form on behalf of Penn State.

Travel reimbursement will not be provided as part of the study protocol.

14.0 Economic Burden to Subjects

14.1 Costs

All tests and procedures required for participation in the study will be paid for by the internal grants. There are no additional costs to subjects participating in the research.

14.2 Compensation for research-related injury

It is the policy of the institution to provide neither financial compensation nor free medical treatment for research-related injury. In the event of an injury resulting from this research, medical treatment is available but will be provided at the usual charge. Costs for the treatment of research-related injuries will be charged to subjects or their insurance carriers.

15.0 Resources Available

15.1 Facilities and locations

Locations for study visits may include the Penn State Women's Health Clinic at Hope Drive and the Clinical Research Center at the Penn State Hershey Medical Center.

The immunoassays will be run by [name]. Her lab is located at [name]. The PK study will be conducted by the lab of [name] and his lab is located at [name]

15.2 Feasibility of recruiting the required number of subjects

The principal investigator sees on average 10 patients each week with endometriosis; approximately 30-40 are seen total with the MIGS practice. Ideally up to 10% of those potential subjects would be interested in this project.

15.3 PI Time devoted to conducting the research

The principal investigator has dedicated research time and is available to see study patients 5 days/week.

15.4 Availability of medical or psychological resources

Resources will be made available at the Penn State Hershey Medical Center if necessary.

15.5 Process for informing Study Team

The PI and study team members will complete required study specific training prior to the start of the trial. Ongoing communication in-person, via email and telephone will also take place.

16.0 Other Approvals

16.1 Other Approvals from External Entities N/A

16.2 Internal PSU Committee Approvals

Check all that apply:

	Anatomic Pathology – Penn State Health only – Research involves the collection of tissues or use of pathologic specimens. Upload a copy of "HRP-902 - Human Tissue For Research Form" in CATS IRB.
	Animal Care and Use – All campuses – Human research involves animals and humans or the use of human tissues in animals
X	Biosafety – All campuses – Research involves biohazardous materials (human biological specimens in a PSU research lab, biological toxins, carcinogens, infectious agents, recombinant viruses or DNA or gene therapy).
X	Clinical Laboratories – Penn State Health only – Collection, processing and/or storage of extra tubes of body fluid specimens for research purposes by the Clinical Laboratories; and/or use of body fluids that had been collected for clinical purposes but are no longer needed for clinical use. Upload a copy of "HRP-901 - Human Body Fluids for Research Form" in CATS IRB.
X	Clinical Research Center (CRC) Advisory Committee – All campuses – Research involves the use of CRC services in any way.
	Conflict of Interest Review – All campuses – Research has one or more of study team members indicated as having a financial interest.
	Radiation Safety – Penn State Health only – Research involves research-related radiation procedures. All research involving radiation procedures (standard of care and/or research-related) must upload a copy of "HRP-903 - Radiation Review Form" in CATS IRB.
X	IND/IDE Audit – All campuses – Research in which the PSU researcher holds the IND or IDE or intends to hold the IND or IDE.
X	Scientific Review – Penn State Health only – All investigator-written research studies requiring review by the convened IRB must provide documentation of scientific review with the IRB submission. The scientific review requirement may be fulfilled by one of the following: (1) external

submission. The scientific review requirement may be fulfilled by one of the following: (1) external peer-review process; (2) department/institute scientific review committee; or (3) scientific review by the Clinical Research Center Advisory committee. NOTE: Review by the Penn State Health Cancer Institute (PSCI) Protocol Review Committee or the PSCI Disease Team is required if the study involves cancer prevention studies or cancer patients, records and/or tissues. For more information about this requirement see the IRB website.

17.0 Multi-Site Study

- 17.1 Other sites N/A
- 17.2 Communication Plans N/A
- 17.3 Data Submission and Security Plan N/A
- 17.4 Subject Enrollment N/A
- 17.5 Reporting of Adverse Events and New Information N/A

17.6 Audit and Monitoring Plans N/A

18.0 Adverse Event Reporting

18.1 Adverse Event Definitions

For drug studies, incorporate the following definitions into the below responses, as written:				
Adverse event	Any untoward medical occurrence associated with the use of the drug in			
	humans, whether or not considered drug related			
Adverse reaction	Any adverse event caused by a drug			
Suspected adverse	Any adverse event for which there is a reasonable possibility that the drug			
reaction	caused the adverse event. Suspected adverse reaction implies a lesser degree			
	of certainty about causality than "adverse reaction".			
	 Reasonable possibility. For the purpose of IND safety reporting, 			
	"reasonable possibility" means there is evidence to suggest a causal			
	relationship between the drug and the adverse event.			
Serious adverse	Serious adverse event or Serious suspected adverse reaction: An adverse event			
event or Serious	or suspected adverse reaction that in the view of either the investigator or			
suspected adverse	sponsor, it results in any of the following outcomes: Death, a life-threatening			
reaction	adverse event, inpatient hospitalization or prolongation of existing			
	hospitalization, a persistent or significant incapacity or substantial disruption			
	of the ability to conduct normal life functions, or a congenital anomaly/birth			
	defect. Important medical events that may not result in death, be life-			
	threatening, or require hospitalization may be considered serious when, based			
	upon appropriate medical judgment, they may jeopardize the patient or			
	subject and may require medical or surgical intervention to prevent one of the			
	outcomes listed in this definition.			
Life-threatening	An adverse event or suspected adverse reaction is considered "life-			
adverse event or	threatening" if, in the view of either the Investigator (i.e., the study site			
life-threatening	principal investigator) or Sponsor, its occurrence places the patient or research			
suspected adverse	subject at immediate risk of death. It does not include an adverse event or			
reaction	suspected adverse reaction that had it occurred in a more severe form, might			
	have caused death.			
Unexpected	An adverse event or suspected adverse reaction is considered "unexpected" if			
adverse event or	it is not listed in the investigator brochure, general investigational plan, clinical			
Unexpected	protocol, or elsewhere in the current IND application; or is not listed at the			
suspected adverse	specificity or severity that has been previously observed and/or specified.			
reaction.				

18.2 Recording of Adverse Events

All adverse events (serious or non-serious) and abnormal test findings observed or reported to study team believed to be associated with the study drug(s) or device(s) will be followed until the event (or its sequelae) or the abnormal test finding resolves or stabilizes at a level acceptable to the investigator.

An abnormal test finding will be classified as an adverse event if one or more of the following criteria are met:

- The test finding is accompanied by clinical symptoms
- The test finding necessitates additional diagnostic evaluation(s) or medical/surgical intervention; including significant additional concomitant drug treatment or other therapy
 NOTE: Simply repeating a test finding, in the absence of any of the other listed criteria, does not constitute an adverse event.

- The test finding leads to a change in study drug dosing or discontinuation of subject participation in the clinical research study
- The test finding is considered an adverse event by the investigator.

18.3 Causality and Severity Assessments

The investigator will promptly review documented adverse events and abnormal test findings to determine 1) if the abnormal test finding should be classified as an adverse event; 2) if there is a reasonable possibility that the adverse event was caused by the study drug(s) or device(s); and 3) if the adverse event meets the criteria for a serious adverse event.

If the investigator's final determination of causality is "unknown and of questionable relationship to the study drug(s) or device(s)", the adverse event will be classified as associated with the use of the study drug(s) or device(s) for reporting purposes. If the investigator's final determination of causality is "unknown but not related to the study drug(s) or device(s)", this determination and the rationale for the determination will be documented in the respective subject's case history.

18.4 Reporting of Adverse Reactions and Unanticipated Problems to the FDA

18.4.1 Written IND/IDE Safety Reports

The Sponsor-Investigator will submit a written IND Safety Report (i.e., completed FDA Form 3500A) to the responsible new drug review division of the FDA for any observed or volunteered adverse event that is determined to be a serious and unexpected, suspected adverse reaction. Each IND Safety Report will be prominently labeled, "IND Safety Report", and a copy will be provided to all participating investigators (if applicable) and sub-investigators.

Written IND Safety Reports will be submitted to the FDA as soon as possible and, in no event, later than 15 calendar days following the Sponsor-Investigator's receipt of the respective adverse event information and determination that it meets the respective criteria for reporting.

For each written IND Safety Report, the Sponsor-Investigator will identify all previously submitted IND Safety Reports that addressed a similar suspected adverse reaction experience and will provide an analysis of the significance of newly reported, suspected adverse reaction in light of the previous, similar report(s) or any other relevant information.

Relevant follow-up information to an IND Safety Report will be submitted to the applicable review division of the FDA as soon as the information is available and will be identified as such (i.e., "Follow-up IND Safety Report").

If the results of the Sponsor-Investigator's follow-up investigation show that an adverse event that was initially determined to not require a written IND Safety Report does, in fact, meet the requirements for reporting; the Sponsor-Investigator will submit a written IND Safety Report as soon as possible, but in no event later than 15 calendar days, after the determination was made.

18.4.2 Telephoned IND Safety Reports – Fatal or Life-threatening Suspected Adverse Reactions In addition to the subsequent submission of a written IND Safety Report (i.e., completed FDA Form 3500A), the Sponsor-Investigator will notify the responsible review division of the FDA by telephone or facsimile transmission of any unexpected, fatal or life-threatening suspected adverse reaction.

The telephone or facsimile transmission of applicable IND Safety Reports will be made as soon as possible but in no event later than 7 calendar days after the Sponsor-Investigator's receipt of

the respective adverse event information and determination that it meets the respective criteria for reporting.

18.5 Reporting Adverse Reactions and Unanticipated Problems to the Responsible IRB

In accordance with applicable policies of The Pennsylvania State University Institutional Review Board (IRB), the investigator will report, to the IRB, any observed or reported harm (adverse event) experienced by a subject or other individual, which in the opinion of the investigator is determined to be (1) unexpected; and (2) probably related to the research procedures. Harms (adverse events) will be submitted to the IRB in accordance with the IRB policies and procedures.

18.6 Unblinding Procedures

The Investigational Pharmacy at Penn State Hershey Medical Center will be responsible for randomization, blinding and unblinding as needed. Investigators will have the discretion of unblinding the physicians at any time if warranted for safety and/or scientific reasons.

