3.3 Early Withdrawal of Subjects

3.3.1 Criteria for removal from study

Subjects will be removed from the study for safety reasons. Subjects will be evaluated for potential negative reactions to study medications at each visit. Additionally, subjects will be advised to contact the study team immediately with any new negative symptoms.

Known severe adverse events of the study drugs will result in the immediate cessation of the study drugs and removal from the study.

- 1. Severe adverse events of NETA include:
 - a. (1) Stroke (2) Deep Vein Thrombosis (3) Pulmonary Embolism (4) Myocardial Infarction (5) Retinal Vein Thrombosis.
 - b. Worsening or persistent migraines will result in cessation of the study drug and therefore, removal from the study.
- 2. Serious adverse events associated with CBD include:
 - a. (1) Suicidal ideation (2) Liver Dysfunction resulting in hepatic failure, hepatic pain that limits self-care activities of daily living, or acute liver damage as measured by LFTS (elevations in ALT or AST > 3 times the ULN and for ALP or TBL > 2 times the ULN)

In the case of an inadvertent pregnancy, the study participant will be immediately withdrawn from the study.

Other adverse events will be monitored and may result in cessation of the study drug and subject withdrawal from the study as determined by the clinical investigator. When possible, we will use the definitions described by the NIH's Common Terminology Criteria for Adverse Events (CTCAE), Version 5, subjects meeting criteria for a Grade 3 CTCAE will be withdrawn from the study if they can be attributed to the study drug. If causality cannot be determined, it will be attributed to the study drug.

Examples:AnemiaGrade 3Hb < 8.0	DiarrheaGrade 3Increase of \geq 7 stools per day over baseline

Withdrawal of consent at any time during the study period will also constitute the withdrawal of a study subject.

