3.3.2 Follow-up for withdrawn subjects

Subjects will be asked to return the study drug to the site if withdrawn from the study.

If the subject was removed for elevated LFTS, these will be followed until resolution and the patient advised to seek medical care if appropriate. If the subject is removed from the study for any of the other reasons as described in 3.3.1, she will receive the appropriate treatment and follow up based on the decision of her providing physician team.

In the case of an inadvertent pregnancy, the study participant will be immediately withdrawn from the study. The participant will be followed through during pregnancy for adverse maternal, fetal and neonatal outcomes that could be appropriately linked back to the study drug.

No further data will be collected on these patients and the subject will not be replaced.

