7.4.3 Method for Assigning Subject to Treatment Groups

The statistician involved in this study will develop the programs necessary for the random number generator to create the randomization. Investigational Drug Services (IDS) will be performing randomization via REDCap to ensure proper blinding of the study team. They will also be responsible for distributing the study medications according to assigned group as per their standard operating procedure.

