7.4.5 Blinding of the Test Article

The norethindrone provided will be in individual identical packets. All study participants will be receiving norethindrone as standard of care treatment for endometriosis and this drug will not be blinded. The placebo, low and high dose CBD will be provided in identical vials. CBD Concentration will be adjusted so that subjects are each receiving equal volume of drug. In addition, CBD oil is usually blended with a carrier oil, such as coconut oil or hemp seed oil. The placebo drug consists of the same carrier oil.

The drug will be kept and dispensed in the Investigational Pharmacy at Penn State Hershey Medical Center and they will hold the randomization and unblinding key as needed. Investigational Drug Services will be responsible for blinding the test drug to the investigators and to the participants.

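### Section 18.6 lets investigators unblind physicians at any time for undefined scientific reasons, a ground that no planned procedure needs

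*Combined protocol and SAP*

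**What the plan says.** Section 18.6 makes the Investigational Pharmacy responsible for randomization, blinding and unblinding. It then adds: "Investigators will have the discretion of unblinding the physicians at any time if warranted for safety and/or scientific reasons".

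Two earlier sections set the default. Section 7.4.3 states: "Investigational Drug Services (IDS) will be performing randomization via REDCap to ensure proper blinding of the study team". Section 7.4.5 states: "Investigational Drug Services will be responsible for blinding the test drug to the investigators and to the participants". Section 7.4.5 also says of the pharmacy that "they will hold the randomization and unblinding key as needed", so the plan expects that codes may sometimes be broken.

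No section says what a scientific reason is, when in follow-up it may be invoked, or which physicians are meant.

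**The concern.** The sentence in Section 18.6 joins two grounds of different kinds. Safety serves the individual participant and is an accepted reason to break a code. A scientific reason serves the trial, and before the data are complete it usually argues for keeping the blind. As written, the second ground is available throughout follow-up at the investigators' discretion.

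What is at stake is the study-team blind. Several decisions that shape the data rest on clinical judgement, and someone who knows the arm may make them differently for placebo and CBD. Section 8.2 says the results will be used to size further studies, and Section 2.2 calls them potential preliminary data for multi-center work. Avoidable doubt about the blind would carry forward into both.

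**Working it through.** No arithmetic settles this point. The check sets the sections side by side.

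**1. Is the scientific ground limited elsewhere?** Sections 7.4.3 and 7.4.5 state the blind and who holds the key. Sections 9.6 to 9.8 and 18.7 cover data review, suspension and stopping without mentioning unblinding. Section 18.3 covers causality without mentioning it. None of them limits the ground.

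**2. Does any planned procedure need the allocation during follow-up?** The candidates are:

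| Candidate use | Section | What the text shows |
|---|---|---|
| CBD dose changes | 7.4.2 | None foreseen |
| Week 8 CBD level | 7.1, 7.2.5 | Drawn at visit 4, when study drug stops; no clinical action during treatment depends on it |
| Optional PK visit | 7.2.7 | Every participant receives the same 20 mg dose, after a 4-week washout |
| Interim testing | 9.7 | Marked not applicable |
| 6-monthly cumulative review | 9.6 | Falls under the Data and Safety Monitoring Plan; not said to be unblinded |

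No stated use remains for the scientific ground.

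**3. Who are the physicians?** For trial staff the protocol usually says study team, investigators or clinical investigator. Elsewhere, physician tends to mean a referring, primary or treating clinician: Section 4.1, Section 7.2.1, and Section 3.3.2, where care after withdrawal is "based on the decision of her providing physician team". The groups may overlap. Section 4.2 recruits mainly from the division's own clinic, and Section 15.2 says the principal investigator sees about 10 endometriosis patients a week. The text leaves the question open.

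**4. If study clinicians are included, which judgements could be affected?**

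- *Adverse-event causality.* The investigator rates it (Sections 9.2 and 18.3).
- *Withdrawal.* Adverse events outside the mandatory list "may result in cessation of the study drug and subject withdrawal from the study as determined by the clinical investigator" (Section 3.3.1). After withdrawal, "No further data will be collected on these patients and the subject will not be replaced" (Section 3.3.2). For Grade 3 events a default narrows the discretion: "If causality cannot be determined, it will be attributed to the study drug". That default works only when causality is undetermined, and a clinician who knows the arm may feel able to determine it.
- *Oxycodone.* Section 7.4.6.1 requires a participant's request and a finding of medical necessity, and Section 8.3 adjusts the pain score for analgesic use.
- *Norethindrone.* Section 7.2.3 names 2 adjustment visits, visits 3 and 4. Study drug stops at visit 4, so 2 − 1 = 1 of them (visit 3, week 4) falls within treatment.

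**5. What does the weekly normalisation in Section 8.3 do?** With D diary days observed, the weekly score is AUC × 7 / D. A completer has D = 8 × 7 = 56. A participant withdrawn at week 4 has D = 4 × 7 = 28. The rescaling makes the two comparable in length. It does not recover the unobserved 56 − 28 = 28 days, so it softens the withdrawal route without closing it.

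**6. When does the exposure end?** Not at week 8. Section 7.2.6 collects surveys, inflammatory markers and adverse events at week 12.

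**7. Size.** The documents do not say how often the ground would be used, who would be told, or how decisions would shift. No bias figure can be calculated.

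**The case against.** A reader might infer that Section 18.6 contradicts Sections 7.4.3 and 7.4.5. It does not: those sections state a default, Section 7.4.5 itself foresees code breaks, and Section 18.6 states the exception. The pharmacy holds the key, and a break must be warranted. This part of the objection stands. Custody of the key, however, does not set a criterion for the decision, which is left to the investigators.

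The routes to harm depend on study clinicians being among the physicians, which is not established. This also stands, and the point is conditional on it. If only outside clinicians are meant, the risk is smaller, though the plan gives them no scientific task that needs the allocation either.

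The routes are also narrow. Known severe events mandate removal. Oxycodone follows only on request, ibuprofen and acetaminophen are bought over the counter, and Section 7.2.3 reads as though a participant who contacts the team for breakthrough pain simply receives the prescription. Norethindrone is adjusted within stated aims. All of this reduces the risk without removing it.

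It can be said that the 6-monthly review covers cumulative data in general, not only safety data. That is true of its wording, but nothing says the review is unblinded. It can also be said that a restriction beyond week 8 is too wide, because the primary endpoint covers only the treatment period. That does not stand, since secondary outcomes and causality ratings are still being collected at week 12.

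**Conclusion.** The point holds as a minor one. Section 18.6 contains an undefined, non-safety ground for breaking the blind that is open throughout follow-up and that no planned procedure uses. Any harm depends on the assumption that the physicians include clinicians who make trial decisions.

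Three stronger readings are not supported:

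- *The primary endpoint is compromised.* Participants enter the VAS themselves and this clause does not unblind them, so clinician rating of pain is not in question. The remaining routes are indirect and cannot be quantified.
- *The double blind is contradicted.* The sections are compatible as a rule and its exception.
- *Code breaks go unrecorded.* The pharmacy works under its own procedures and institutional policy, which are not part of these documents, so the absence of a record is unknown.

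The trial randomizes 36 participants, 12 per arm at 1:1:1, uses mainly descriptive methods and has no power calculation. The issue is therefore one of trial conduct and credibility, not of error rates.

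**What to change.** Delete the words 'and/or scientific reasons' from Section 18.6. Alternatively, keep the scientific ground but allow it only after the last week 12 visit and database lock. Leave safety unblinding exactly as written, including any safety review behind a pause or stop under Sections 9.8 and 18.7.

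The cost is one changed sentence. Sample size, visits and analyses are unaffected. The only downside is that investigators lose an exception that no planned procedure uses.
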